3.3 Patient Reported Outcome (PRO) Variables

PRO variables will be assessed using the European Organization for Research and Treatment of Cancer (EORTC) 30-item core quality of life questionnaire (QLQ-C30) with the lung cancer module (QLQ-LC-13) (health-related quality of life [HRQoL] with lung cancer specific additional concerns), EQ-5D-5L, Patient's Global Impression of Severity (PGIS), and PRO-CTCAE. All items/questionnaires will be scored according to published scoring guidelines or the developer's guidelines, if published guidelines are not available. All PRO analyses will be based on the FAS, unless otherwise stated. PRO questionnaires will be collected as per the assessment schedule in Table 1 of the CSP, up until study termination, PFS2 (as defined in Section 3.2.8) or death. Rules for handling multiple records are detailed in Section 4.1.2.

3.3.1 EORTC QLQ-C30 and QLQ-LC13

The EORTC QLQ-C30 consists of 30 questions that are grouped into 5 multi-item functional scales (physical, role, cognitive, emotional, and social), 3 multi-item symptom scales (fatigue, pain, and nausea/vomiting), 5 single items assessing additional symptoms commonly reported

by cancer patients (dyspnea, insomnia, appetite loss, constipation, and diarrhea), a 2-item global measure of health status/quality of life (GHS/QoL), and a single item on the financial impact of the disease. The GHS/QoL will be assessed using 2 items from the QLQ-C30: "How would you rate your overall health during the past week? (Item 29) and "How would you rate your overall QoL during the past week? (Item 30). The EORTC QLQ-C30 will be scored according to the EORTC QLQ-C30 scoring manual (Fayers et al 2001).

The QLQ-LC13 is a lung cancer specific module from the EORTC for lung cancer comprising 13 questions to assess lung cancer symptoms (cough, hemoptysis, dyspnea, and site-specific pain), treatment-related side-effects (sore mouth, dysphagia, peripheral neuropathy, and alopecia), and pain medication. With the exception of a multi-item scale for dyspnea, all are single items. The dyspnea scale will only be used if all 3 items have been scored; otherwise, the items are treated as single-item measures.

All items are scored between 1 ("not at all") to 4 ("very much") with the exception of the 2 GHS/QoL items which are scored 1 ("very poor") to 7 ("excellent"). An outcome variable consisting of a transformed score from 0 to 100 will be derived for each of the symptom scales/symptom items, the functional scales and the GHS/QoL scale in the QLQ-C30 and for each of the symptom scales/items in the QLQ-LC13 according to the EORTC QLQ-C30 Scoring Manual (Fayers et al 2001) and EORTC QLQ-LC13 instructions.

Higher scores on the GHS/QoL and functional scales indicate better health status/function, but higher scores on symptom scales/items represent greater symptom severity. For each subscale, if <50% of the subscale items are missing, then the subscale score will be divided by the number of non-missing items and multiplied by the total number of items on the subscales (Fayers et al 2001). If at least 50% of the items are missing, then that subscale will be treated as missing. Missing single items are treated as missing. The reason for any missing questionnaire will be identified and recorded. If there is evidence that the missing data are systematic, missing values will be handled to ensure that any possible bias is minimized. Rules for handling multiple records are detailed in Section 4.1.2.

Functional and symptom scale derivations

The EORTC QLQ-C30 functional and symptom scales, individual symptom items and global health status are derived as follows.

1. Calculate the average of the items that contribute to the scale or take the value of an individual item, i.e. the raw score (RS):

$$RS = (I_1 + I_2 + ... + I_n) / n,$$

where $I_1 + I_2 + ... + I_n$ are the items included in a scale and n is the number of items in a scale.

2. Use a linear transformation to standardize the raw score, so that scores range from 0 to 100, where a higher score represents a higher ("better") level of functioning, or a higher ("worse") level of symptoms.

Functional scales: Score = $(1 - [RS - 1] / range) \times 100$

Symptom scales/items; global health status: Score = $([RS - 1] / range) \times 100$,

where *range* is the difference between the maximum and the minimum possible value of RS.

The scoring approach for the EORTC QLQ-LC13 is identical to that for the symptom scales / single items of the QLQ-C30. The number of items and item range for each scale/item are displayed in Table 5.

Table 5 Scoring of the EORTC QLQ-C30 and QLQ-LC13

Scale/ item	Scale/ item abbreviation	Number of items (n)	Item range	Item numbers
QLQ-C30				
Global health status/QoL	QL2	2	6	29, 30
Functional scales				
Physical	PF2	5	3	1-5
Role	RF2	2	3	6, 7
Cognitive	CF	2	3	20, 25
Emotional	EF	4	3	21-24
Social	SF	2	3	26, 27
Symptom scales				
Fatigue	FA	3	3	10, 12, 18
Pain	PA	2	3	9, 19
Nausea/ vomiting	NV	2	3	14, 15

Symptom items

DY SL	1	3	
SL			8
	1	3	11
AP	1	3	13
CO	1	3	16
DI	1	3	17
FI	1	3	28
LCDY	3	3	3,4,5
LCCO	1	3	1
LCHA	1	3	2
LCSM	1	3	6
LCDS	1	3	7
LCPN	1	3	8
LCHR	1	3	9
LCPC	1	3	10
LCPA	1	3	11
LCPO	1	3	12
	CO DI FI LCDY LCCO LCHA LCSM LCDS LCPN LCHR LCPC LCHR LCPC	CO 1 DI 1 FI 1 LCDY 3 LCCO 1 LCHA 1 LCSM 1 LCDS 1 LCPN 1 LCPN 1 LCPN 1 LCHR 1 LCHR 1 LCHR 1 LCPC 1 LCPA 1	CO 1 3 DI 1 3 FI 1 3 LCDY 3 3 LCCO 1 3 LCHA 1 3 LCSM 1 3 LCDS 1 3 LCPN 1 3

EORTC European Organisation for Research and Treatment of Cancer; QLQ-C30 30-item core quality-of-life questionnaire; QoL Quality of life.

^{*}Not reported on in the analysis.

Baseline will be defined as described in Section 4.1.2.

The following 5 PRO measures have been identified as primary from the EORTC QLQ-C30 and EORTC QLQ-LC13, namely:

- Dyspnea (multi-item scale based on three questions: "Were you short of breath when you rested; walked; climbed stairs?" QLQ-LC13)
- Cough: one item ("How much did you cough?" QLQ-LC13)
- Chest pain: one item ("Have you had pain in your chest?" QLQ-LC13)
- Fatigue (multi-item scale based on three questions: "Did you need rest; Have you felt weak; Were you tired?" QLQ-C30)
- Appetite loss: one item ("Have you lacked appetite?" QLQ-C30)

Furthermore, physical functioning, role functioning, and GHS/QoL domains of the EORTC QLQ-C30 are pre-specified endpoints of interest (FDA, 2021).

Definition of clinically meaningful changes

Changes in score compared with baseline will be evaluated. A minimum clinically meaningful change is defined as an absolute change in the score from baseline of ≥ 10 for scales/items from the EORTC QLQ-C30 and the QLQ-LC13 (). For example, a clinically relevant deterioration in chest pain (as assessed by QLQ-LC13) is defined as an increase in the score from baseline of ≥ 10 . A clinically relevant improvement in fatigue (as assessed by QLQ-C30) is defined as a decrease in the score from baseline of ≥ 10 . At each post-baseline assessment, the change in symptoms/functioning from baseline will be categorized as improvement, no change, or deterioration as shown in Table 6.

Table 6 Visit responses for symptoms and HRQoL

Score	Change from baseline	Visit response
QLQ-C30/QLQ-LC13 symptom	≥+10	Deterioration
scales/items	≤-10	Improvement
	>-10 to <+10	No change
QLQ-C30 functional scales and	≥+10	Improvement
GHS/QoL	≤-10	Deterioration
	>-10 to <+10	No change

GHS/QoL Global health status/Quality of life; HRQoL Health-related quality of life; QLQ-C30 30-Item core quality of life questionnaire; QLQ-LC13 Lung cancer module.

For the visit level summaries of Improvement/Deteriorated/No change then all patients with a baseline and post-baseline score will be included thus the denominator may differ from the time to deterioration and improvement rate endpoints derived below.

3.3.1.1 Time to QLQ-C30 and QLQ-LC13 symptom deterioration

For each of the symptoms scales/items in the QLQ-C30 and QLQ-LC13, time to symptom deterioration will be defined as the time from randomization until the date of the first clinically meaningful symptom deterioration (an increase in the score from baseline of \geq 10) that is confirmed at the next available assessment at least 14 days apart or death (by any cause) in the absence of a clinically meaningful symptom deterioration, regardless of whether the patient withdraws from study treatment or receives another anticancer therapy prior to symptom deterioration (i.e. date of symptom deterioration event or censoring – date of randomization + 1). Missed visits are allowed in between assessments confirming deterioration. This is considered a conservative approach whereby a deterioration is considered a 'negative' outcome and therefore should be assigned as such, regardless of missed visits.

Death will be included as an event only if the death occurs within 2 visits of the last PRO assessment (and where there were no previous 2 consecutive missed visits) where the symptom change could be evaluated. Patients with a single deterioration and no further assessments will be treated as deteriorated in the analysis.

Patients whose symptoms (as measured by QLQ-C30 and QLQ-LC13) have not shown a clinically meaningful deterioration and who are alive at the time of the analysis will be censored at the time of their last PRO assessment where the symptom could be evaluated, or prior to 2 consecutive missed visits if 2 missed visits are observed. Also, if symptoms deteriorate after 2 or more missed PRO assessment visits or the patient dies after 2 or more consecutive missed PRO assessment visits, the patient will be censored at the time of the last PRO assessment where the symptom could be evaluated, prior to the 2 missed assessment visits. The 2 missed visit rule for ePRO will take a 'look-forward' approach i.e. if there are 2 consecutive missed visits at any time prior to the confirmed deterioration event, the event will be censored at the last available assessment prior to the 2 missed visits. If the patient has no evaluable visits or does not have baseline data, they will be censored at Day 1 unless they die within 2 visits of baseline. Confirmation of deterioration will first be determined, then the censoring rules will be applied to assess if any determined deterioration can be used or if it needs to be censored earlier due to 2 missed visits..

See Appendix B for further details on the derivation of the confirmation of deterioration 2-missed visit rule for ePRO and length of 2 missed visit window.

The population for analysis of time to symptom deterioration will include a subset of the FAS who have baseline scores ≤ 90 .

In this analysis, RECIST 1.1 progression will not be considered as symptom deterioration and data will not be affected by RECIST 1.1 progression.

3.3.1.2 Time to QLQ-C30 GHS/QoL/functional deterioration

For GHS/QoL and functional deterioration, time to deterioration will be defined as the time from the date of randomization until the date of the first clinically meaningful deterioration (a

decrease in the functional scales or the GHS/QoL from baseline of ≥ 10) that is confirmed at the next available assessment at least 14 days apart, or death (by any cause) in the absence of a clinically meaningful deterioration , regardless of whether the patient withdraws from study treatment or receives another anticancer therapy prior to GHS/QoL and functional deterioration (i.e. date of GHS/QoL/functional deterioration event or censoring – date of randomization + 1). Missed visits are allowed in between assessments confirming deterioration. This is considered a conservative approach whereby a deterioration is considered a 'negative' outcome and therefore should be assigned as such, regardless of missed visits.

Death will be included as an event only if the death occurs within 2 visits of the last PRO assessment (and where there were no previous 2 consecutive missed visits) where the GHS/QoL/function change could be evaluated (prior to the 2 missed assessment visits, Appendix B). Patients with a single deterioration and no further assessments will be treated as deteriorated in the analysis.

Patients whose GHS/QoL/function (as measured by QLQ-C30) have not shown a clinically meaningful deterioration and who are alive at the time of the analysis will be censored at the time of their last PRO assessment where the GHS/QoL/function could be evaluated, or prior to 2 missed visits if 2 missed visits are observed. Also, if GHS/QoL/function deteriorates after 2 or more missed PRO assessment visits or the patient dies after 2 or more missed PRO assessment where the symptom could be evaluated. The 2 missed visit rule for ePRO will take a 'look-forward' approach i.e. if there are 2 consecutive missed visits at any time prior to the confirmed deterioration event, the event will be censored at the last available assessment prior to the 2 missed visits. If the patient has no evaluable visits or does not have baseline data, they will be censored at Day 1 unless they die within 2 visits of baseline. Confirmation of deterioration will first be determined, then the censoring rules will be applied to assess if any determined deterioration can be used or if it needs to be censored earlier due to 2 missed visits.

See Appendix B for further details on the derivation of the confirmation of deterioration, 2-missed visit rule and length of 2 missed visit window.

The population for analysis of time to GHS/QoL/function deterioration will include a subset of the FAS who have baseline scores ≥ 10 .

In this analysis, RECIST 1.1 progression will not be considered as GHS/QoL/function deterioration and data will not be affected by RECIST 1.1 progression.

3.3.1.3 QLQ-C30 and QLQ-LC13 symptom improvement rate

The symptom improvement rate will be defined as the number (%) of patients with a minimum of 2 consecutive assessments at least 14 days apart that show a clinically meaningful improvement (a decrease from baseline score ≥ 10 for symptom scales/items) in that symptom from baseline. Missed visits are not allowed in between consecutive assessments of improvement. This is considered a conservative approach whereby an

improvement is considered a 'positive' outcome and therefore for any avoidance of doubt in the assessment of an improvement, missed visits are not allowed.

When the assessment schedule is weekly i.e. QLQ-LC13 weeks 1 to 8, an improvement needs to be observed at each assessment that falls within the 14 day interval to be classed as an improvement. For example:

V1	V2	V3	V4	Outcome
(Week 1)	(Week 2)	(Week 3)	(Week 4)	
IMP	IMP	IMP	NC	Improvement
IMP	IMP	NC	DT	No improvement*
IMP	MV	IMP	IMP	No improvement*
NC	IMP	NC	IMP	No improvement*

DT Deterioration; IMP Improvement; MV Missed visit. NC No change.

The denominator will consist of a subset of the FAS who have a baseline symptom score ≥ 10 .

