# Improvement rate

A summary of the symptom improvement rate for all symptom scales/items in EORTC QLQ-C30 and QLQ-LC13 will be produced. Similarly, a summary of function/HRQoL improvement rate for each of the 5 function scales (physical, role, emotional, cognitive, and social) and global health status/QoL will be produced.

Symptom improvement rates will be analyzed by comparing between treatment groups using a logistic regression model. The odds ratio and 95% CI for each scale/item will be presented graphically on a Forest plot. If there are very few responses in 1 treatment group, a Fisher's exact test will be considered.

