3.3.1.4 QLQ-C30 GHS/QoL/functional improvement rate

The GHS/QoL/functional improvement rate will be defined as the number (%) of patients with 2 consecutive assessments at least 14 days apart that show a clinically meaningful improvement (an increase from baseline score ≥10 for functional scales and GHS/QoL) in that scale from baseline. Missed visits are not allowed in between consecutive assessments of improvement. This is considered a conservative approach whereby an improvement is considered a 'positive' outcome and therefore for any avoidance of doubt in the assessment of an improvement, missed visits are not allowed.

The denominator will consist of a subset of the FAS who have a baseline score <90.

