Symptom, functional and GHS/QoL improvement rates will be analyzed by comparing between treatment groups using a logistic regression model adjusting for the same factors as the PFS endpoint. The results of the analysis will be presented in terms of an odds ratio together with its associated profile likelihood 95% CI and p-value (based on twice the change in log-likelihood resulting from the addition of a treatment factor to the model). The odds ratio and 95% CI for each scale/item will be presented graphically on a forest plot. If there are very few responses in 1 treatment group, a Fisher's exact test will be considered.

Change from baseline

Summaries of original and change from baseline values of each symptom scale/item, the GHS/QoL score, and each functional domain will be reported by assessment timepoint for each treatment group. Graphical presentations may also be produced as appropriate. Summaries of the number and percentage of patients in each response category at each assessment timepoint for each ordinal item (in terms of the proportion of patients in the categories of improvement, no change, and deterioration as defined in Table 6) will also be produced for each treatment group.

A summary of compliance rate and evaluability rate will be provided for each treatment group, by assessment time point and also for overall. The summary will be provided for the FAS, combination analysis set, and patients who have discontinued treatment.

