- For any assessments where the visit schedule changes from $q1w \pm 3$ days to $q4w \pm 3$ days, the maximum time between two consecutive assessments is 3+7+28+3=41 days
- For any assessments where the visit schedule is $q4w \pm 3$ days, the maximum time between two consecutive assessments is 3+28+28+3=62 days

^{*}Missed visits are allowed in between assessments confirming deterioration and confirmation of deterioration requires at least 14 days between assessments (which should take into account the weekly assessment schedule for the QLQ-LC13 for the first 8 weeks).

Length of 2 missed visit window for EORTC QLQ-C30

The scheduled visit assessments and visit windows for the QLQ-C30 are 4 weekly (±3 days) relative to randomization until study termination, PFS2 or death.

Missing baseline or within 2 visits of baseline:

- A patient without baseline will be censored at day 1 unless they die \leq day 59.
- Any assessment ≤ day 59 is within 2 visits (8 weeks + 3 days) of baseline and therefore cannot be censored for missing visits.

Schedule: q4w:

• For any assessment > day 1 the visit schedule is $q4w \pm 3$ days and thus the maximum time between two consecutive assessments is 3+28+28+3=62 days (8 weeks + 6 days).

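### The QLQ-C30/QLQ-LC13 improvement rates have no observation window common to both arms, so the odds ratio can mix symptom change with time observed

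*SAP*

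**What the plan says.** For symptom scales and items the SAP counts the "number (%) of patients with a minimum of 2 consecutive assessments at least 14 days apart that show a clinically meaningful improvement" (SAP 3.3.1.3). For the functional scales and global health status it counts "patients with 2 consecutive assessments at least 14 days apart that show a clinically meaningful improvement" (SAP 3.3.1.4). Neither section states when counting ends. The footnote to the worked example in 3.3.1.3 makes its non-improver rows depend on there being no later assessments, so later visits can turn a non-improver into an improver.

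Collection runs "up until study termination, PFS2 (as defined in Section 3.2.8) or death" (SAP 3.3). After the first 8 weeks both questionnaires are four-weekly; for the core questionnaire Appendix B says that the visits for "the QLQ-C30 are 4 weekly (±3 days) relative to randomization until study termination, PFS2 or death".

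The comparison is made by "comparing between treatment groups using a logistic regression model adjusting for the same factors as the PFS endpoint" (SAP 4.2.11.1). It reports an odds ratio, a profile-likelihood interval, a likelihood-ratio p-value and a forest plot. No term represents time observed. Protocol 9.5.1.9 also specifies the model for symptoms: "Symptom improvement rates will be analyzed by comparing between treatment groups using a logistic regression model". For function and global health, Protocol Table 13 plans description only, whereas SAP Table 7 lists logistic regression. The SAP amendment history records this as a correction, but SAP Section 6 does not list it as a change from the protocol.

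The other PRO analyses in SAP 4.2.11.1 limit or account for follow-up. The mixed model stops at progression, death or 24 months, and deterioration is a censored time-to-event outcome tested by log-rank.

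**The concern.** An ever/never outcome gives a patient one more chance to qualify at each extra visit. The number of visits is set by PFS2, death and study termination, and the first two are outcomes that the drug is meant to postpone. Equal symptom processes therefore imply equal ever-improved proportions only when follow-up is also equal.

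The secondary objective concerns symptoms and health-related quality of life. If follow-up is longer on durvalumab, part of a PFS2 or survival benefit could reappear as an apparent symptom benefit. Going by SAP Table 5, this could affect about 24 scales and items (14 from the QLQ-C30 without the financial item, 10 from the QLQ-LC13), each with its own odds ratio. Under equal symptoms the shift always favours the arm followed longer.

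**Working it through.** **The design's own effects.** No power or error rate is stated for the improvement rate. The planned PFS and OS effects show how far follow-up may be expected to differ, so I reproduced them first, with power = Φ(√d/2·|ln HR| − z).
- OS: 348 deaths, HR 0.73, final two-sided level 3.616% (Protocol 9.6): 9.327 × 0.3147 − 2.095 = 0.840, power 0.80. Stated: 80%.
- PFS: 370 events, HR 0.65, level 0.444%: power 0.903. Stated: about 90%.
- Medians: 10/0.65 = 15.4 months; 24/0.73 = 32.9 months. Both agree with the SAP.

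**Closed form, to show the mechanism.** Let confirmed improvement occur at the same constant rate λ in both arms, and let collection stop at rate μ = ln 2/median. Over a window T,

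P(improved) = λ/(λ+μ) × [1 − exp(−(λ+μ)T)].

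Take OS-like stopping (24 vs 32.9 months), λ = 0.03 per month (assumed) and 131 evaluable patients per arm (assumed 50% of 262).
- No window: μ = 0.0289 and 0.0211, so P = 0.510 and 0.587. The difference is 0.078, its standard error 0.061 and z = 1.27. The two-sided 5% test rejects with probability Φ(1.27 − 1.96) = 0.245.
- 24-week window (T = 168/30.4375 = 5.52 months): P = 0.141 and 0.144, z = 0.07, rejection 5.1%.

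For λ from 0.01 to 0.2 and 131 to 262 per arm, the unwindowed rejection rate is 12 to 43% with OS-like stopping and 10 to 24% at 16 vs 20 months. These figures are high because the formula has no data cut-off and no missed visits.

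**Visit-level simulations, same symptom process in both arms.** PFS2 medians are not in the documents; 16 months on placebo is assumed. The first set has four-weekly visits, 80% compliance, 38-month accrual plus 24 months, about 131 evaluable per arm and 400 trials per cell (Monte Carlo standard error near 10%: √(0.10×0.90/400) = 1.5 points). The second set uses a two-state model with probability 0.06 of entering and 0.35 of leaving the improved state per visit, with 105 or 157 per arm (assumed 40% or 60% of 262).

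| Follow-up medians (months) | Rejection at nominal 5% |
|---|---|
| 16 vs 16 | 3.5–4.8% (first set); 4–5% (second) |
| 16 vs 20 | 9–12% (first) |
| 16 vs 21.9 | 13–18% (first) |
| 16 vs 23 | 17% with 105 per arm, 25% with 157 (second) |
| 24 vs 32.9 | 11–14% (first); 12–16% (second) |

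Repeat runs of the 16 vs 23 cell with 157 per arm and full compliance reached 28%, so the upper end is approximate.

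**Timing of improvement.** If improvement can occur only in the first 3 months, rejection is 5–6%; in the first 6 months, 5–8%. If the chance of improving halves every 3 months (16 vs 23, 157 per arm), it is 5.5–8%. Halving every 6 months gave 6–9% in one run and 7–15% in another. Halving every 12 months gave 12–23%.

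**Remedies on the same null data.** A 24-week window gave 4–6%. A 6-month window gave about 4.5–8% for PFS2-like or OS-like stopping. A log-rank test on time to first confirmed improvement gave 4–7.5% in the first set. A 24-month cap alone still gave 6–41% in the closed form (16 months on placebo, HR 0.65 to 0.73).

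**The case against.** The strongest reply is that nothing is wrong with the test. It compares the proportions of patients who ever have a confirmed improvement while observed. If durvalumab prolongs observation those proportions differ, and rejecting a false null is not a type I error. This stands: the problem is what the odds ratio means, not the validity of logistic regression.

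The excess is also conditional. It needs later PFS2 or death on durvalumab, and improvements that continue well into follow-up. Baseline falls within 42 days after chemoradiotherapy, so early recovery is plausible, and then little excess remains. This stands too.

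The stakes are limited. Protocol 9.5.1.9 makes the mixed model the primary PRO analysis, treats those endpoints as supportive and applies no multiplicity adjustment. The improvement rate is not in the multiple testing procedure (SAP 4.2.1).

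A reader might infer more: that follow-up is unlimited, that the test rejects too often in general, or that rates of 25–35% apply, as simulated with PFS-like stopping (10 vs 15.4 months). The documents support none of these. Collection ends at study termination, PFS2 or death; with equal follow-up the rate is about 5%; and collection does not stop at first progression.

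What survives is that no common window is set, no rationale is given for leaving it out, and nothing elsewhere in the SAP repairs this endpoint.

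**Conclusion.** The point holds as a conditional interpretation bias in a supportive endpoint. The improvement rate has no window common to both arms and its analysis ignores time observed, so its odds ratio combines symptom change with length of observation. If PFS2 or death comes later on durvalumab and improvements keep accruing, the nominal 5% test rejects about 9–25% of the time under equal symptoms, in favour of durvalumab. If improvement is mostly early the figure is about 5–9%; with equal follow-up it is about 5%.

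These sizes rest on assumed PFS2 medians, improvement rates and timing, evaluable share and compliance; the documents give none of them. The structural gap itself needs no assumption. The controlled error rate for PFS and OS is not affected.

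**What to change.** In SAP 3.3.1.3 and 3.3.1.4, count improvement only within a fixed window from randomization that is the same for both arms, for example the first 24 weeks. In SAP 4.2.11.1, apply the logistic regression, odds ratio, interval and p-value to that outcome. Keep the unrestricted ever-improved percentage as description, without an odds ratio or p-value.

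Time to first confirmed improvement may be added as a supportive analysis. It should state that censoring at PFS2 and death is assumed non-informative. It should not replace the logistic model, which the protocol specifies for symptoms. Borrowing the mixed model's limits would not be enough: a 24-month cap leaves much of the dependence, and a stop at progression ties follow-up to PFS, where the planned gap between arms is 10 vs 15.4 months.

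The cost is SAP wording and one reprogrammed derivation, with no new data. Improvements after the window no longer count, and a small dependence on very early stopping remains.
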